#### **3.7.2 Definition of Study Baseline**

Unless otherwise noted, study baseline is defined as the last observation obtained prior to administration of the first dose on Study Day 1.

Change from baseline is defined as post-baseline assessment minus baseline assessment. The baseline value will not be used to impute the post-baseline values.

#### **3.7.3 Unscheduled Visits**

The CRF nominal study visits will be used for all safety analyses. Unscheduled visits will be reflected in summarization of changes to worst post-baseline measures.

Additionally, for missing scheduled assessments with an unscheduled assessment available after the previous scheduled visit but before the next scheduled visit, the closest unscheduled assessment will be used in the place of missing scheduled efficacy assessments

All unscheduled visits will be listed.

### **3.8 Rounding**

The method of rounding for data presentation is provided in [Appendix 3](#).

## 4. BASELINE CHARACTERISTICS AND PATIENT DISPOSITION

### 4.1 Disposition of Patients

A disposition summary will include:

- Number and percentage of patients randomized in each cohort
- Number and percentage of patients in the safety analysis set
- Number and percentage of patients completing treatment
- Number and percentage of patients discontinuing treatment
- Number and percentage of patients by reason for discontinuing treatment
- Number and percentage of patients completing study
- Number and percentage of patients terminating study
- Number and percentage of patients by reason for terminating study

Disposition summaries will be presented by randomized treatment. Percentages will be based on the number of randomized patients.

A listing of patient disposition will include the randomization date, date of the last dose of study drug, study completion status, and reason for termination (if applicable).

### 4.2 Demographics and Baseline Characteristics, Baseline Disease Characteristics, and Radiation Treatment Plan

Demographic and baseline characteristics summaries, for patients in the safety analysis set, will include:

- Age (years at study baseline)
- Sex
- Race
- Ethnicity
- Smoking status
- Fitzpatrick skin Type

Baseline disease characteristics will be provided in a separate summary. Continuous statistics will be provided for:

- Time since diagnosis (years)
- Time since surgery (days)

- Breast volume after surgery (cc)
- Chest wall separation (cm)

Frequency tables (number and percentage) will be provided for discrete measures:

- Breast cancer treatment prior to radiation therapy
- Breast cancer stage
- T/N/M clarification
- Post-mastectomy reconstruction
- Prior receipt of radiation treatment

Radiation treatment plan will be provided in a separate summary. Continuous statistics will be provided for:

- Total planned radiation (Gy)
- Total planned radiation boost (Gy)
- Total radiation (regular + boost) (Gy)
- Planned bolus use (days)
- Radiation treatment surface area (cm^2)
- Radiation inhomogeneity (%)

Frequency tables (number and percentage) will be provided for discrete measures:

- Planned radiation treatment area

All will be summarized by randomized treatment group without stratification and stratified by smoking status and breast cancer treatment prior to radiation therapy, respectively.

#### **4.3 Study Drug Exposure**

Study treatment exposure (i.e. RTA 408 Lotion 0.5%, RTA 408 Lotion 3%, or vehicle lotion), including treatment duration will be summarized by treatment group with descriptive statistics. Similarly, the incremental and cumulative radiation exposure will be summarized by treatment group. The number of patients with interruptions in radiation treatment due to radiation tolerability will be tabulated overall and by study visit. Total study treatment exposure for each patient is calculated as follows: (last date of study treatment) – (first date of study treatment) + 1. Additionally, treatment compliance will be summarized, and the number of treatment compliant patients (i.e.,  $\geq 75\%$  compliant with dosing) will be tabulated. Compliance is calculated as [(total exposure days) – (total missed doses)] / (total exposure days).

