^b Visit 2 (7 days prior to radiation treatment) is the day of randomization and application of the first dose, and must occur at least 5 and no more than 9 days prior to the first day of radiation treatment. If the start of radiation treatment is delayed, patients should continue administering study drug twice daily until the first dose of radiation up to a maximum of 14 days. If the time from randomization to first dose of radiation exceeds 14 days, the medical monitor should be contacted to decide on an appropriate action. Patients may be randomized after meeting the inclusion / exclusion criteria and before study drug lotion is first administered as long as patients apply study drug lotion for at least 5 days prior to the first day of radiation treatment. Patients with either morning or afternoon randomizations may apply lotion in the clinic and again before bedtime for two doses on that day.

^c Visit 3 should occur on the day of the first radiation treatment. If radiation treatment is in the morning, the radiation treatment will be the third to last procedure (radiation treatment > study drug application > PK). If radiation treatment is in the afternoon, radiation treatment will be the second to last procedure, and the last procedure will be PK, as study drug will have been applied at least 4 hours prior to radiation treatment.

^d Study visits during radiation treatment therapy must occur weekly beginning with Day 1 of radiation treatment.

^e At the end of radiation treatment, patients must complete Visit 9 assessments. Visit 9 must be the last day of the 10 – 16 Gy boost. Visit 8 is needed for patients who require radiation therapy for 6 weeks. If radiation therapy is extended longer than 6 weeks, then assessments at Visit 8 should be repeated weekly until the end of radiation visit (Visit 9). A weekly study visit should not be performed if the visit falls 1 or 2 days prior to the last day of radiation (Visit 9), or 1-2 days after the last day of radiation.

^f Visit 10 should occur approximately 1 week (7 calendar days) after the completion of radiation therapy (Visit 9).

^g Visit 11 should occur approximately 1 week (7 calendar days) after Visit 10 (*i.e.*, 2 weeks after the completion of radiation therapy).

^h Follow-up visit will occur approximately 4 weeks after the final study drug application. These procedures should be performed at the end of study and for early termination.

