9.3. Treatment Compliance

The investigator or his/her designated and qualified representatives will only dispense study drug to patients enrolled in the study in accordance with the protocol. Study drug is to be dispensed to the patients at the scheduled study visits. Additional study drug will be dispensed to patients based on patient need and will be recorded as an unscheduled study drug dispensation. The study drug must not be used for reasons other than that described in the protocol. A maximum of 14 consecutive missed doses (7 days of twice daily dosing) or no more than 28 total non-consecutive missed doses are permitted during the study. Additionally, a maximum of 6 total missed doses is permitted in the 7 day run-in period prior to the start of radiation treatment. Patients who exceed the number of allowed missed doses will be considered not compliant with dosing and will have a protocol deviation recorded, but these patients will be encouraged to continue with dosing and will not be discontinued from the study.

In cases where radiation treatment is delayed (*e.g.*, delayed start of radiation treatment or radiation treatment interruptions), the study drug application period may be extended from the expected 8-9 weeks up to a maximum of 13 weeks. If the start of radiation treatment is delayed, patients should continue administering study drug twice daily until the first dose of radiation up to a maximum of 14 days. If the time from randomization to first dose of radiation exceeds 14 days, the medical monitor should be contacted to decide on an appropriate action.

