9.8.13. Study Drug Administration

Patients may be randomized after meeting the inclusion / exclusion criteria and before study drug lotion is first administered, as long as patients apply study drug lotion for at least 5 days prior to the first day of radiation treatment. Patients should self-administer the lotion at the time points indicated in Table 3. Study drug is to be applied twice daily. The amount of lotion used will depend on the size of the radiation treatment area. On days of morning radiation treatments, the patient will apply the study drug at the radiation treatment center immediately after the radiation

therapy concludes and at night before bed. On days of afternoon radiation treatments, the patient will apply the study drug in the morning at least 4 hours before radiation treatment and at night before bed. A thin layer of lotion will be applied to the indicated or planned radiation treatment area, which includes any regional irradiated lymph nodes. RTA 408 Lotion or vehicle lotion should never be applied immediately before radiation treatment, and any residual lotion from a prior application should be removed prior to radiation treatment. On the last day of study drug administration, patients will only have a morning study drug application as the study drug will be collected that day. If patients develop grade 2 or higher radiation dermatitis and the radiation dermatitis is believed to be inadequately controlled in the opinion of the Investigator, additional topical creams, lotions, hydrocortisone or other escape medications may be prescribed and then must be documented. Patients should continue study drug administration in addition to escape medications prescribed by the Investigator. Patients should apply escape medications 1-3 hours after study drug application. Any residual escape medication should be removed prior to study drug application.

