## 1.2 Study Design

This randomized, double-blind, vehicle-controlled, parallel-group study will assess the safety, tolerability and efficacy of RTA 408 Lotion (0.5% or 3%) versus vehicle in the treatment of patients at risk for radiation dermatitis. Eligible patients will be randomized using a 1:1:1 assignment ratio to receive RTA 408 Lotion 0.5%, RTA 408 Lotion 3%, or vehicle 1 week ( $\pm$  2 days) prior to initiation of radiation therapy. Randomization will be stratified by smoking status (smoker or ex-smoker versus non-smoker) and breast cancer treatment prior to radiation therapy (mastectomy versus lumpectomy/partial mastectomy).

Study drug application will start approximately 1 week prior to scheduled initiation of radiation therapy with twice daily applications continuing throughout the duration of radiation therapy (i.e., 5-6 weeks) and two weeks following completion of radiation therapy, for an expected total of up to 9 weeks of study drug application. In cases where radiation treatment is delayed (e.g., delayed start of radiation treatment or radiation treatment interruptions), the total study drug application period may be extended from the expected 8-9 weeks up to a maximum of 13 weeks. Study lotion is to be applied twice daily.

On days of morning radiation treatments, the patient will apply the study drug at the radiation treatment center immediately after the radiation therapy concludes and at night before bed. On days of afternoon radiation treatments, the patient will apply the study drug in the morning at least 4 hours before radiation treatment and at night before bed. For each application of study drug treatment, a thin layer of lotion will be applied to the irradiated area. RTA 408 Lotion or vehicle lotion should never be applied immediately before radiation treatment, and any residual lotion from a prior application should be removed prior to radiation treatment.

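### The SAP compliance formula subtracts missed doses from exposure days under twice-daily dosing, which about doubles the missed fraction and turns the 75% cut into about 87.5%

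*SAP*

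**What the plan says.** SAP 4.3 first defines exposure in calendar days: "Total study treatment exposure for each patient is calculated as follows: (last date of study treatment) – (first date of study treatment) + 1". It then gives the compliance rule, "Compliance is calculated as [(total exposure days) – (total missed doses)] / (total exposure days", and plans to tabulate how many patients reach at least 75%.

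Dosing is twice a day in both documents; SAP 1.2 has "Study lotion is to be applied twice daily", and protocol 9.8.13 agrees. Protocol 9.3 shows what a missed dose is: "A maximum of 14 consecutive missed doses (7 days of twice daily dosing". It also sets a total allowance, "no more than 28 total non-consecutive missed doses are permitted during the study", and a limit of six missed doses in the run-in week. On breaching these limits it says: "Patients who exceed the number of allowed missed doses will be considered not compliant with dosing and will have a protocol deviation recorded".

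Two further passages bear on how many doses are due. For the first day, footnote b of the protocol's schedule of assessments says that patients "may apply lotion in the clinic and again before bedtime for two doses on that day". For the last day, protocol 9.8.13 says: "On the last day of study drug administration, patients will only have a morning study drug application".

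**The concern.** The numerator takes a count of doses away from a count of days, and the denominator is in days. With two doses due per day, each missed application is charged as a full missed day. The resulting percentage is not the share of doses taken, although it is compared with a 75% threshold described as compliance with dosing.

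At stake are the planned by-arm compliance summary and the count of compliant patients. The mean missed fraction in each arm, and any difference between arms in that mean, would be about doubled. A reader using these tables to judge whether the lotion was actually applied in each arm would be misled. SAP 1 says that the SAP prevails where it and the protocol differ on planned analyses, so a programmer would have to implement the formula as written.

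**Working it through.** **Inputs**

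- D = exposure days, last date minus first date plus 1 (SAP 4.3).
- m = missed doses, each a single application (protocol 9.3: 14 doses are 7 days).
- Doses due per day: 2 (SAP 1.2, protocol 9.8.13).
- Compliance cut: 75% (SAP 4.3).
- Application period: 8 to 9 weeks expected, 13 weeks at most (protocol 9.3), so D = 56, 63 and 91.
- Total missed-dose allowance: 28 (protocol 9.3).

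The SAP gives no worked compliance value to reproduce, so the formulas are compared directly.

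**Formulas**

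- SAP as written: (D − m)/D, missed fraction m/D.
- Dose basis: (2D − m)/(2D), missed fraction m/(2D).
- Dose basis with one dose on the last day: (2D − 1 − m)/(2D − 1).

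**Overstatement of the missed fraction.** Against 2D doses the ratio is (m/D)/(m/(2D)) = 2 for any m above 0. Against 2D − 1 it is (2D − 1)/D: 111/56 = 1.982, 125/63 = 1.984 and 181/91 = 1.989.

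**Effective cut.** The SAP formula passes when m/D is at most 0.25. That is m/(2D) at most 0.125, so the cut in doses taken is 1 − 0.125 = 87.5%.

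**Most missed doses that still pass 75%** (rounded down)

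| D | SAP, 0.25 × D | 2D doses, 0.5 × D | 2D − 1 doses, 0.25 × (2D − 1) | Below 75% by the SAP but at least 75% of 2D doses, within 28 missed |
|---|---|---|---|---|
| 56 | 14 | 28 | 27 | 15–28 |
| 63 | 15 | 31 | 31 | 16–28 |
| 91 | 22 | 45 | 45 | 23–28 |

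Under the 2D − 1 convention the 56-day band is 15–27.

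**Examples**

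| D | m | SAP formula | Dose basis, 2D |
|---|---|---|---|
| 56 | 15 | 41/56 = 73.2% | 97/112 = 86.6% |
| 63 | 16 | 47/63 = 74.6% | 110/126 = 87.3% |
| 91 | 23 | 68/91 = 74.7% | 159/182 = 87.4% |
| 56 | 28 | 28/56 = 50.0% | 84/112 = 75.0% |
| 63 | 28 | 35/63 = 55.6% | 98/126 = 77.8% |
| 91 | 28 | 63/91 = 69.2% | 154/182 = 84.6% |
| 63 | 70 | −7/63 = −11.1% | 56/126 = 44.4% |

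**Boundary behaviour**

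- A patient with 28 missed doses passes the SAP cut only if D is at least 28/0.25 = 112 days, beyond the 91-day maximum.
- A patient who applies once a day throughout has m = D and scores 0%, with half the doses taken.
- When m exceeds D the score is negative.
- A patient whose only missed doses are one run of 14 still passes: 42/56 = 75.0% and 49/63 = 77.8%.
- With no missed dose, both formulas give 100%.

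**The case against.** The strongest objection is that little depends on this figure. Efficacy is analysed in all randomized patients, the safety population needs only one dose, no per-protocol population is defined, and compliance is not a planned covariate. Exceeding the protocol's limits leads to a recorded deviation, not to discontinuation. Individual data are listed, a diary is kept and bottles are weighed, so the correct figure could be recovered later. All of this stands, and it limits the reach of the error. It does not make the planned table right.

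The miscount is also conditional. The percentage is wrong for every patient with a missed dose, but the count of compliant patients changes only if someone falls in an affected band. The bands use the 28-dose total alone. A patient with 15 to 28 missed doses may already breach the limit on consecutive doses or the run-in limit, and would then be non-compliant under the protocol too. Both qualifications stand.

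One could read missed doses as missed days, which would make the formula coherent. Protocol 9.3 rules this out by equating 14 missed doses with 7 days.

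Finally, the protocol's fixed count and the SAP's percentage are different measures and need not agree. That is fair. Their similar wording calls for distinct labels and is only a side point here.

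**Conclusion.** The concern holds. As written, the formula overstates the missed fraction twofold (1.98 to 1.99 with a single dose on the last day) for every patient with a missed dose, and its 75% cut requires about 87.5% of doses taken. Patients within the 28-dose total would be tabulated below 75% from 15, 16 or 23 missed doses at 56, 63 or 91 days, although at least 75% of their doses were taken. The one exception is exactly 28 missed at 56 days, which is 75.0% or 74.8% on a dose basis depending on how the last day is counted.

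This rests on two applications being due each day and on a missed dose being one application, both stated in the documents. The number of patients affected cannot be estimated. The consequence is confined to the descriptive compliance summary and the count of compliant patients; the primary test and the safety analyses are untouched. It should be corrected before the tables are programmed.

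**What to change.** In SAP 4.3, replace the formula with compliance = (scheduled doses − missed doses) / scheduled doses, where scheduled doses = 2 × exposure days. State how the first and last days are counted, including for patients who stop early. The choice matters only at the margin: 28 missed at 56 days is 84/112 = 75.0% with 2 × days and 83/111 = 74.8% with one dose fewer.

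Label the SAP's 75% threshold and the protocol 9.3 missed-dose limits as separate measures, or reconcile them. They will still differ after the unit correction: 29 to 31 missed doses at 63 days, or 29 to 45 at 91 days, meet 75% but exceed the protocol's total of 28.

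The cost is one line in the SAP and in the program, plus the counting convention and the label. Missed doses are already an input, so no new data are needed.

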#### **4.4 Inclusion and Exclusion Criteria**

A listing will be provided for all randomized patients who did not meet all study entry criteria as defined by inclusion and exclusion criteria.

#### **4.5 Medical History**

Medical history will be coded using MedDRA, version 16.0 or higher. Medical history will be summarized by SOC and PT, and will be presented by treatment. Percentages will be based on the number of patients in the safety analysis set. Medical history tables will be sorted alphabetically and all data will be listed chronologically.

#### **4.6 Prior and Concomitant Medications**

Prior and concomitant medications will be coded using the World Health Organization (WHO) drug dictionary (December, 2012) for anatomical therapeutic chemical classification (ATC) and preferred drug name. A patient who used multiple medications will be counted only once for each ATC and preferred drug name. ATC and preferred drug name within each ATC will be sorted alphabetically. Coded prior and concomitant medications will be summarized by treatment. Percentages will be based on the number of patients in the safety analysis set.

Prior medications are defined as those medications disclosed as not being taken on Study Day 1 on the CRF, with an onset date prior to the date of randomization. Concomitant medications are defined as any medications that was either taken on or after Study Day 1, or was started before Study Day 1 but was ongoing at time of the first dose administration.

#### **4.7 Protocol Deviations**

Protocol deviations as captured on the CRF will be listed. All protocol deviations will be reviewed by the Sponsor according to their SOPs. Major protocol deviations will be identified by the Sponsor prior to database lock, and will be flagged in the listing.

## 5. EFFICACY ANALYSIS

The primary population for efficacy analyses will include all randomized patients in this trial (intent-to-treat population, ITT population). The ITT analysis will be done by randomized treatment, and for each patient subset of interest defined in section 3.4.

Summary statistics will be presented by randomized treatment group, and will include an additional column to summarize the pooled RTA 408 patients.

### 5.1 Primary Efficacy

The primary efficacy outcome of this study is the radiation dermatitis grade measured with Common Terminology Criteria for Adverse Events (CTCAE, Version 4.03) following 3D conformal radiation therapy to the breast and concomitant administration of RTA 408 Lotion (0.5% and 3%) compared to administration of vehicle. Radiation dermatitis scoring is assessed by a local, trained physician, nurse or appropriately trained site staff member based on CTCAE v4.03 on a scale of 0 to 5 (National Cancer Institute, 2010). Following randomization, patients will be evaluated in person at weekly visits during the administration of the study treatment up to a maximum of 13 weeks.

Longitudinal mixed-models will be used to analyze the dermatitis scores over time, incorporating the repeated measures design of the study. Treatment group and week of visit will constitute the main fixed effects of the model; study subject will represent the random effect; site, smoking status, and breast cancer treatment will be evaluated for inclusion in the model as covariates. The distribution of residuals will be examined using a Shapiro-Wilks test. Interactions of time and treatment effect will also be examined in the mixed-model.

A sensitivity analysis will be performed using the same model, except cumulative radiation (expressed as a categorical variable in 2.5 Gy increments from 0 to 70 Gy) will be used as a fixed effect instead of visit week. Only those CTCAE grades collected from baseline to the last day of radiation treatment for each patient will be considered for this sensitivity analysis.

The mean CTCAE dermatitis scores will also be plotted in a scatter plot by cumulative radiation exposure overall and by patient subsets of interest.

RTA 408 treatment arms will be compared with vehicle utilizing a hierarchical testing strategy described in Section 3.6.

